8.2.2.1. Complete Case Analysis of the DOOR at Outcome Assessment Visit #1

Analysis will be performed as described in Section 8.2.2 using the CC-V1 population. Ordinal clinical response values, number of days of antibiotic use, and DOOR at outcome assessment visit #1 of CC-V1 subjects will be presented in [Listing 19](#).

8.2.2.2. Complete Case Analysis of the DOOR at Outcome Assessment Visit #2

Analysis will be performed as described in Section 8.2.2 using the CC-V2 population. Ordinal clinical response values, number of days of antibiotic use, and DOOR at outcome assessment visit #2 of CC-V2 subjects will be presented in Listing 19.

8.2.2.3. According-to-Protocol Analysis of the DOOR at Outcome Assessment Visit #1

Analysis will be performed as described in Section 8.2.2 using the ATP-V1 population.

8.2.2.4. According-to-Protocol Analysis of the DOOR at Outcome Assessment Visit #2

Analysis will be performed as described in Section 8.2.2 using the ATP-V2 population.

8.2.2.5. Worst Case Analysis of the DOOR at Outcome Assessment Visit #1

Analysis will be performed as described in Section 8.2.2 using the ITT population with missing values imputed as follows. Subjects in the short course arm will have their ordinal clinical response imputed as 8 and their number of days of antibiotic use imputed if missing (see Section 6.5.6) as 0. As an exception, subjects in the short course arm with OCR missing for Outcome Assessment Visit #1 but not for Outcome Assessment Visit #2 will have the OCR for Outcome Assessment Visit #1 imputed as the Outcome Assessment Visit #2 value or as 5, whichever value is larger. Subjects in the standard course arm will have their ordinal clinical response imputed as the value that would occur if all missing data was benign (no additional solicited events / cough / fever, etc.) and their number of days of antibiotic use imputed if missing (see Section 6.5.6) as 5.

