- Oral, rectal, axillary, or tympanic temperature $\geq 38.3^{\circ}\text{C}$ (100.9°F), confirmed by repeat measurement after at least 15 minutes, in the 24 hours preceding the Outcome Assessment Visit, unless attributed to a new process that is unrelated to the prior diagnosis of pneumonia;

- Elevated respiratory rate (RR >50 breaths/minute for children <24 months of age and >40 breaths/minute for children 24-71 months of age) at the time of the Outcome Assessment Visit;

- Presence of cough grade 2 or 3 at the Outcome Assessment Visit, defined as Grade 0 (no cough), Grade 1 (Occasional coughing [less than 4 times hourly]), Grade 2 (frequent coughing [4 or more times an hour], interferes with sleep), Grade 3 (almost constant coughing (never free of cough), makes sleep nearly impossible);

³ Solicited events will be captured daily until Outcome Assessment Visit #2; thereafter, parents/legal guardians will report symptoms based on memory aid and medical interview by study staff. For those with multiple solicited events, the ordinal response table will be based upon the most severe solicited event.

Day 1: Day 1 begins at the time the first dose of study product is administered and ends at 11:59 PM of that same day. If a subject has no recorded receipt of study product at the time of the analysis, then Day 1 will be defined as the date 5 days after the date of initiation of the initial antibiotic.

DOOR at Outcome Assessment Visit #1: Defined as above, using DOOR components from the following Study Days.

Adequate Clinical Response: Day 1 – Day 5

Resolution of Symptoms:

- o Fever as measured in the 24 hours prior to Outcome Assessment Visit #1. If a subject has a fever according to a single measurement, but no repeat measurement after at least 15 minutes has been performed, the subject will be analyzed as having a fever. If a subject has a fever according to the measurement taken as a part of vital signs

during Outcome Assessment Visit #1, the subject will be analyzed as having a fever at Outcome Assessment Visit #1. If the vital signs measurement shows no fever, and the parental assessment of fever during the previous 24 hours is missing, then fever will be treated as missing.

- o Respiratory Rate and Cough: determined at Outcome Assessment Visit #1

Solicited Events: Day 1 – Day 5

Number of Days of Antibiotic Use: Day 1 – Day 5

DOOR at Outcome Assessment Visit #2: Defined as above, using DOOR components from the following Study Days.

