6.3.1. Intention-to-Treat Analysis (ITT) Cohort

The ITT cohort will include all randomized subjects that were still eligible on Day 1 of the study. The analyses on the ITT cohort will be performed per randomized treatment assignment.

Randomized subjects who became ineligible before Day 1 of the study and did not take any study product will be excluded from ITT. Subjects randomized but not treated for other reasons other than ineligibility will be analyzed in the ITT cohort, but will have adequate clinical response and its components treated as missing. Therefore, in ITT analyses, OCR and DOOR will be missing and will need to be imputed for subjects that were not treated. If data (solicited events, cough, etc.) are collected post-randomization for a subject that was not treated, that data will be used in the ITT analysis to assist in imputing the OCR and DOOR.

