6.5. Missing Data

While all efforts will be made to minimize missing data, some missing data is expected. Whenever possible, subjects terminating from the study early will be given an early termination visit during which the available components of the DOOR and related measures can be recorded. The primary analysis will use multiple imputation with linear models to impute values using available information (treatment, randomization strata variables, and available visit information), assuming a missing at random (MAR) model. Secondary analyses will further examine the robustness of this analysis, including a “worst case analysis” in which all imputations of missing

data will be the worst case (result in the lowest possible DOOR given available information) for subjects in the 5-day arm and best case for subjects in the 10-day arm. Day 1 in this study is defined as the date of first receipt of study product. If a subject has no record of study product administration or did not receive a first dose of study product, but has other post-randomization data, Day 1 will be imputed as the date 5 days after the date of first receipt of initial antibiotic.

In some cases, a subject may have DOOR defined despite missing some of its components, in which case the subject will be eligible for inclusion into the CC and ATP analysis populations. In analyses of the components of the DOOR using the CC and ATP analysis populations, data will be analyzed as available and missing data will not be imputed.

The study includes several composite variables with rules for assignment, missingness, and imputation described below.

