6.5.6. Number of Days of Antibiotic Use at OAV#1 or OAV#2

It will be assumed that all subjects have precisely five days of antibiotic use with the initial antibiotic prior to Day 1 (the day of the first dose of study product). Analysis involving comparisons of the number of days of antibiotic use will consider antibiotic use from Day 1 onwards. The number of days of antibiotic use is defined as the actual number of days of antibiotic use (any amount of study product that is not placebo, or any amount of other systemic antibiotic) from Day 1 to Day 5, inclusive, for OAV#1 and from Day 1 to Day 18 for OAV#2. For subjects that received placebo as study product, it is counted as the number of days of systemic antibiotic as determined solely from the concomitant medication form. For subjects that receive actual antibiotic as study product, it is counted as the number of days that the subject received any amount of either study product or a non-study systemic antibiotic, as determined

from the concomitant medication form. Note that missed doses of study product do not necessarily lower the number of days of antibiotic use as long as a separate dose of antibiotic (study product antibiotic or concomitant medication antibiotic) was received on that day. Extra doses of study product beyond the protocol specification of 10 doses count as normal toward the number of days of antibiotic use. The number of days of antibiotic use is missing (at both OAV#1 and OAV#2) if the product administration record was not completed / on record for the subject and the subject did not have antibiotic use during the study period recorded as a concomitant medication. If a subject does not have an OAV#1 or OAV#2, then number of days of antibiotic use at OAV#1 is missing. If a subject does not have an OAV#2, then number of days of antibiotic use at OAV#2 is missing. As exceptions, subjects that were hospitalized due to pneumonia or a complication of pneumonia or the died during the study period will have number of days of antibiotic use at OAV#1 or OAV#2 as 5 if randomized to the standard course or as 0 if randomized to short course if the number of days of antibiotic use at OAV#1 or OAV#2 is missing as defined above.

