13. SUMMARY OF CHANGES IN THE CONDUCT OF THE STUDY OR PLANNED ANALYSES

Changes in the Conduct of the Study

Enrollment into the study was initiated under protocol version 2.0. Substantive changes to the protocol after study initiation are provided below.

Substantive changes in protocol version 3.0

- Removed 200mg/5mL amoxicillin and 200mg/5mL amoxicillin-clavulanate as possible dose strengths under Protocol Section 6.1.2. No subjects were prescribed under this dose.
- Clarified timing of interim analysis to be after at least 30% of the targeted subjects have completed the study instead of approximately 30%.

Changes to the Planned Analyses

There are no changes to the planned analyses as described in the protocol.

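### The worst-case DOOR analysis imputes missing antibiotic days in the opposite direction to its own definition, so it is less adverse to short course than stated when standard-course children have no recorded dose

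*SAP*

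**What the plan says.** SAP 6.5 and Protocol 11.4.2 (Secondary Analyses) give the same rule for all missing data in the worst-case analysis. Imputed values are to "result in the lowest possible DOOR given available information) for subjects in the 5-day arm and best case for subjects in the 10-day arm". SAP 3.3 and 6.5.7 settle the direction of the tie-breaker: at equal OCR, fewer antibiotic days is better, implemented as a score of OCR + days/100 with lower scores better.

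SAP 8.2.2.5 carries this out for Outcome Assessment Visit #1. Missing OCR is set to 8 for short course (with an exception that uses the larger of 5 and the Visit #2 value) and to the benign value for standard course. Short-course children then have "their number of days of antibiotic use imputed if missing (see Section 6.5.6) as 0" and standard-course children have "their number of days of antibiotic use imputed if missing (see Section 6.5.6) as 5". SAP 8.2.2.6 uses the same 0 and 5 at Visit #2.

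Three other provisions matter:

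- SAP 6.3.1: "Subjects randomized but not treated for other reasons other than ineligibility will be analyzed in the ITT cohort", with adequate clinical response treated as missing.
- SAP 6.5.6: days are missing "if the product administration record was not completed / on record for the subject" and no concomitant antibiotic is recorded, or when the outcome visit did not take place. For children who died or were hospitalised for pneumonia, missing days are instead filled "as 5 if randomized to the standard course or as 0 if randomized to short course".
- SAP 13: "There are no changes to the planned analyses as described in the protocol".

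**The concern.** The OCR half of the imputation follows the definition and the days half runs against it. In the Day 1-5 window, 5 is the worst possible value for a standard-course child and 0 the best possible for a short-course child. At Visit #2, where the window is Days 1-18, 5 is no longer the worst value for standard course, but it is still not the best.

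This is the only planned DOOR analysis that departs from missing-at-random against short course. The note to SAP Table 14 says conclusions must take the sensitivity analyses into account, and SAP 6.6 sends this one to the DSMB if the interim test crosses p<0.001. If it is milder than its label says, it can overstate how robust a positive result is, and the error can only favour short course.

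**Working it through.** **Plan's own figures.** The documents give no figure for the worst-case rule. The ranking example in SAP 6.5.7 (scores 1.05, 1.00, 2.00, 1.05) reproduces as ranks 2.5, 1, 4, 2.5, so the scoring is read correctly here.

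**Which children are affected.**

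1. *Standard course, no recorded dose, days missing under 6.5.6.* With nothing adverse observed, the benign OCR is 1. The SAP rule scores the child 1.05, which loses to every short-course child at 1.00. The best case consistent with the records is 0 days, score 1.00, a tie. Each such pair moves from a full win for short course to half a win.
2. *Standard course, at least one recorded dose.* Because "Day 1 begins at the time the first dose of study product is administered", the minimum is 1 day, score 1.01. This still loses to 1.00, so the estimate does not move. This is exact only if every short-course child at OCR 1 has 0 days; antibiotics for an unrelated diagnosis would make it approximate.
3. *Short course, OCR imputed as 8.* The child already ranks below everyone unless a standard-course child died, so 0 versus 5 days changes nothing to four decimals. It matters only at a shared OCR level. If 5 of 200 short-course children fall under the OCR-5 exception with days missing, and 10% of standard-course children are at OCR 5, the effect is 0.5 × (5/200) × 0.10 = 0.00125.

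**Inputs.** From SAP 5: 200 per arm and about 10% loss to follow-up, used here as the missing share *m* in each arm. Assumed, because the documents do not give them: *f*, the share of missing standard-course children with no recorded dose; *q* = P(OCR = 1); the rest of the OCR distribution; the same OCR distribution in both arms; observed days of 0 (short) and 5 (standard); no deaths. The four OCR 1-7 spreads are .35/.25/.15/.05/.15/.04/.01, .45/.22/.10/.03/.15/.04/.01, .60/.18/.07/.02/.10/.02/.01 and .75/.10/.04/.01/.07/.02/.01.

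**Formulas.** Let S be the sum of squared OCR probabilities. Among observed pairs short course wins every OCR tie, so A = (1 + S)/2.

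- SAP rule: (1−m)²A + m(1−m)q
- Defined worst case: (1−m)²A + m(1−m)q(1 − f/2)
- Gap: f × 0.5 × m(1−m) × q

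For q = 0.45 and m = 0.10: S = 0.286 and A = 0.643. The SAP rule gives 0.81 × 0.643 + 0.09 × 0.45 = 0.561. The defined worst case at f = 1 gives 0.521 + 0.09 × 0.225 = 0.541.

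| q | A (no missing data) | SAP rule | Defined, f = 1 | Gap, f = 1 |
|---|---|---|---|---|
| 0.35 | 0.617 | 0.531 | 0.516 | 0.016 |
| 0.45 | 0.643 | 0.561 | 0.541 | 0.020 |
| 0.60 | 0.704 | 0.624 | 0.597 | 0.027 |
| 0.75 | 0.790 | 0.707 | 0.673 | 0.034 |

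Over the same range of q, f = 0.5 gives 0.008-0.017, f = 0.25 gives 0.004-0.008 and f = 0 gives 0. With m = 5% and f = 1 the gap is 0.008-0.018.

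**Can it change a conclusion?** The standard error is about 0.028. With whole-number counts at q = 0.45 and the standard tie-corrected variance, the SAP rule gives 0.562 (95% CI 0.506-0.618). The definition gives 0.557 (0.501-0.613) at f = 0.25, 0.552 (0.496-0.608) at f = 0.5 and 0.541 (0.486-0.597) at f = 1. Simulating 4,000 trials per scenario at m = 10%, the share with a significant result was:

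- q = 0.45: 58% under the SAP rule; 57%, 50%, 43% and 28% under the definition at f = 0, 0.25, 0.5 and 1.
- q = 0.35, f = 1: 18% versus 5.5%.
- q = 0.60, f = 1: 99.5% versus 94%.
- q = 0.75: no change.

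**The case against.** The best defence is that 0 and 5 are a deliberate convention. SAP 6.5.6 already uses them for hospitalised or deceased children, 8.2.2.5 cites that section, and available information might be taken to include the assigned regimen, with the extreme swing placed on OCR. But neither document says this, and the reading fails for a child known not to have been dosed, who would be credited with five days of antibiotic.

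Several limits do stand:

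- The analysis is still severe. At q = 0.45 and f = 1 it delivers (0.643 − 0.561)/(0.643 − 0.541), about 80%, of the defined drop. Over the four spreads the share is 71-84% at f = 1 and 91-96% at f = 0.25.
- *f* and the OCR spread are assumptions. Loss to follow-up is not the same as having no recorded dose: early termination visits include memory-aid review (Protocol 7.5), so some early leavers will have recorded doses. The significance rates are illustrative and move most near the boundary.
- The DSMB sees the analysis only after the ITT test has crossed its boundary, as guidance. The worst-case OCR analyses in 8.2.6.7 and 8.2.6.8 do not use days at all.

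These points limit the size of the problem. They do not remove the mismatch.

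**Conclusion.** The concern holds. SAP 8.2.2.5 and 8.2.2.6 do not implement the worst case that Protocol 11.4.2 and SAP 6.5 define, and SAP 13 declares no change. At Visit #1 nearly all the effect comes from the value of 5 for standard-course children with no recorded dose. It runs from essentially zero (f = 0) to an upper bound of 0.016-0.034 (f = 1) on the probability scale, at 10% missing per arm and 35-75% of children at OCR 1. At the upper end that is about one standard error, enough to change the sensitivity result when it lies near the boundary. No size was worked out for Visit #2. The textual mismatch is certain; its consequence depends on *f* and the OCR distribution, which the documents do not give. The primary test, sample size and power are unaffected. It should be fixed, but it does not threaten the main analysis.

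**What to change.** In SAP 8.2.2.5, impute missing days as the maximum consistent with recorded use for short course (5 if nothing is recorded) and the minimum consistent with recorded use for standard course (0 if no dose is recorded, at least 1 if any dose is). Apply the same logic over Days 1-18 in 8.2.2.6. State that the 0/5 fill-in for hospitalised or deceased children in 6.5.6 does not apply in these two analyses.

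Alternatively, keep the values, rename the analysis as worst-case OCR with assigned antibiotic days, and declare the departure from Protocol 11.4.2 in SAP 13.

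Either way the cost is SAP wording only. Under the first option the sensitivity result becomes equally or slightly less favourable to short course.

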8.2.2.6. Worst Case Analysis of the DOOR at Outcome Assessment Visit #2

Analysis will be performed as described in Section 8.2.2 using the ITT population with missing values imputed as follows. Subjects in the short course arm will have their ordinal clinical response imputed as 8 and their number of days of antibiotic use imputed if missing (see Section 6.5.6) as 0. Subjects in the standard course arm will have their ordinal clinical response imputed as the value that would occur if all missing data was benign (no additional solicited events / cough / fever, etc.) and their number of days of antibiotic use imputed if missing (see Section 6.5.6) as 5.

8.2.3. Solicited Events at Outcomes Assessment Visits #1 and #2

Separately for Outcome Assessment Visit #1 and #2, using CC-V1 and CC-V2, respectively, a forest plot of 95% confidence intervals for the risk difference of each solicited event and the risk difference of any solicited, for each severity threshold (mild or greater, moderate or greater, or severe) will be produced (Figure 3, Figure 4, Figure 5 and Figure 6, Figure 7, Figure 8). Results will also be reported in tables (Table 18, Table 19, Table 20, Table 21, Table 22, and Table 23), and tests for differences in proportions between treatment arms will be given by Fisher's exact tests. The Newcombe method with continuity correction will be used to compute all 95% confidence intervals for risk differences.

8.2.4. Resolution of Symptoms at Outcomes Assessment Visits #1 and #2

Separately for Outcome Assessment Visit #1 and #2, using CC-V1 and CC-V2, respectively, a forest plot of 95% confidence intervals for the risk difference of lack of resolution of symptoms as well as the following: (1) fever (as defined in Section 6.5.2) (2) Elevated respiratory rate (RR >50 breaths/minute for children <24 months of age and >40 breaths/minute for children 24-71 months of age) at the time of the Outcome Assessment Visit; and (3) Presence of cough Grade 2 or 3 at the Outcome Assessment Visit will be given (Figure 9 and Figure 10). Results will also be reported in tables (Table 24 and Table 25), and tests for differences in proportions between treatment arms will be given by Fisher's exact tests. The Newcombe method with continuity correction will be used to compute all 95% confidence intervals for risk differences.

8.2.5. Adequate Clinical Response at Outcomes Assessment Visits #1 and #2

Separately for Outcome Assessment Visit #1 and #2, using CC cohorts, a forest plot of 95% confidence intervals for the risk difference of adequate clinical response as well as the following interventions for persistent or worsening pneumonia: (1) ED/clinic visits, (2) hospitalizations, (3) surgical procedures, and (4) non-study systemic antibiotics will be given (Figure 11 and Figure 13). Results will also be reported in tables (Table 26 and Table 28), and tests for differences in proportions between treatment arms will be given by Fisher's exact tests. The Newcombe method with continuity correction will be used to compute all 95% confidence intervals for risk differences.

Separately for Outcome Assessment Visit #1 and #2, using CC cohorts, a forest plot of 95% confidence intervals for the risk difference of the following interventions for any reason: (1) ED/clinic visits, (2) hospitalizations, (3) surgical procedures, and (4) non-study systemic antibiotics will be given (Figure 12 and Figure 14). Results will also be reported in tables (Table 27 and Table 29), and tests for differences in proportions between treatment arms will be given by Fisher's exact tests. The Newcombe method with continuity correction will be used to compute all 95% confidence intervals for risk differences.

